Primary Endpoints	
1. TICI using NEWS Score [Time Frame: First treatment date up to discharge day (PI's discretion as per patients health condition)]
 
The median time in days from the start of treatment with the study drug / placebo to the persistent achievement of all of the following criteria:
 
 • Stopping a fever (which is defined as a decrease in axillary temperature below 37 ° C without the use of anti pyretic drugs); • Respiratory rate <22 /min; • Oxygen saturation (SPO2) > 95% when breathing in atmospheric air. Measured using pulse oximetry • Systolic blood pressure ≤200mmHg • Pulse rate 51-90beats/minute • Is conscious and alert 
[Note: Persistent achievement means the preservation of each of the criteria for at least 7days.]
 
2. TTIC using 7-point ordinal scale
 
3. Rate of progression to severe/critical COVID-19 disease based on NEWS score [Time frame: First treatment date up to 15days]
 
4. Rate of progression to severe/critical COVID-19 disease based on 7-point ordinal scale [Time frame: First treatment date up to 28days]
 
5. Time to COVID-19 nucleic acid testing negativity in oropharyngeal/nasal swab) [Time Frame: First treatment date up to 28days]

Secondary Endpoints	
 1. Incidence of ICU admissions [Time Frame: 28days] 2. Subject survival rate [Time Frame: 28days] 3. Incidence of mechanical ventilation due to COVID-19 infection [Time Frame: First treatment date up to 28days] 4. Change in clinical or laboratory assessment of comorbid condition [Time Frame: First treatment date up to 28days] 5. Percent of participants with worsening comorbid condition [Time Frame: First treatment date up to 28days] 6. Proportion of subjects in the treatment arm who had AE, SAE 7. Proportion of subjects in the placebo arm who had AE, SAE
Subject Selection Criteria	
Inclusion criteria
 
 1. 50 years or older

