	
 2. Both male and female subjects will be included 3. Positive oropharyngeal/nasal swab RT-PCR for Sars-Co- V2. Diagnosed not more than 2 days ago (diagnosis ≤ 2 days). 4. Either asymptomatic or have mild symptoms. Onset of symptoms within no more than 4 days. If symptomatic, symptoms are mild (cough, weakness, sore throat, low grade fever 38.50°C, respiratory rate should not be more than 22 / min, resting SpO₂ $>95\%$, normal highly sensitive C-reactive protein (HS-CRP) ($<10\text{mg/L}$). There are no signs of dehydration, sepsis or shortness of breath. 5. Chronic stable medical conditions: diabetes mellitus, or hypertension, or chronic heart disease. Under treatment and controlled by medication 6. Signed informed consent/or consent given through text message, WhatsApp or e-mail. 7. Ability to understand the requirements of the Research Protocol and follow the research procedures. 8. Subject should be willing to be managed in isolation wards 9. Negative pregnancy test (for female participants) 10. Adequate contraception for study duration 
Exclusion criteria
 
 1. Less than 50 years 2. With severe COVID-19 symptoms requiring immediate hospitalization 3. Investigator considers the subject unsuitable for ViraCide 4. History of symptoms of more than 4 days 5. COVID-19 diagnosed >2 days ago using oropharyngeal/nasal swab RT-PCR for Sars-Co-V2 6. History of cardiopulmonary resuscitation

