	
Note:
 
*Hematology: Complete blood count (CBC); erythrocyte sedimentation rate (ESR)
 
*Biochemistry:
 
 • Random Blood Sugar, • Serum Creatinine • SGOT, SGPT • Alkaline Phosphatase • Bilirubin-Total/Direct/Indirect • Total Proteins/Albumin/Globulin/A:Gratio • Low density lipoprotein (LDL) Cholesterol(Direct) • LDH • Total Cholesterol • Triglycerides • High Sensitive C-reactive protein(HS-CRP) • BUN (Blood Urea Nitrogen) /Urea • Serum Calcium • Serum Sodium • Serum Potassium • Uric Acid 
*X-ray PA view is an optional test at screening. It may be done

	
at any other time during the study if deemed necessary by the Investigator
 
*Urine pregnancy test (for females only) at screening
 
Note: If subject is discharged before Day 15 PI's discretion as per patients health condition, then assessments scheduled for Day 15 will be carried out on the discharge day (as far as possible and those not performed will be noted on appropriate CRF page) and Day 15 visit will be done telephonically.

Standard of Care Therapy	
SOC therapy for coronavirus infection (COVID-19, SARS-CoV-2) has not been developed yet. Treatment will be given as per the discretion of the PI or as per the guidelines issued by the GOI. GOI guidelines can be accessed here: https://www.mohfw.gov.in/

Concomitant Medications Allowed by the Protocol	
 1. Medications for Diabetes Mellitus 2. Medications for hypertension 3. Statins 4. Blood thinners like aspirin at PI discretion 5. Any medication deemed necessary by the PI to manage the AE/SAE 6. Any other medication deemed necessary by the PI to manage a comorbid condition that is not likely to affect the treatment Protocol
Prohibited Concomitant Medications	Any other herbal medicine or dietary supplement
Statistical Analysis	
Sample size of total 112(56 cases in each arm) completed cases needed to assess the study objective at 80% power and 5% level of significance.
 
Considering 10 % dropout total 124 (62 cases in each arm) cases will be enrolled in this study.

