5. Time to COVID-19 nucleic acid testing negativity in oropharyngeal/nasal swab) [Time Frame: First treatment date up to 28 days]

Confidential & Proprietary

The unauthorized use, disclosure, distribution or copying of these information is strictly prohibited

Secondary Efficacy Endpoints:

1. Incidence of ICU admissions [Time Frame: 28 days]
2. Subject survival rate [Time Frame: 28 days]
3. Incidence of mechanical ventilation [Time Frame: First treatment date up to 28 days]
4. Time to COVID-19 nucleic acid testing negativity in oropharyngeal/nasal swab) [Time Frame: Days 1, 7, 15]
5. Change in clinical or laboratory assessment of comorbid condition [Time Frame: First treatment date up to 28 days]
6. Percent of participants with worsening comorbid condition [Time Frame: First treatment date up to 28 days]

Safety Endpoints

1. Proportion of subjects in the treatment arm who had AE, SAE
2. Proportion of subjects in the placebo arm who had AE, SAE

Confidential & Proprietary

Any unauthorized use, disclosure, distribution or copying of these information is strictly prohibited

3 Analysis sets

Per protocol subset (PP)

Subjects without any Major protocol violation would be included in the per-protocol population, including those subjects who have completed all the visits, who did not take any prohibited medications during the study period and whose CRF was completed as requested.

Modified Intention to treat subset (mITT)

The term “mITT” includes all randomized subjects who met all inclusion/exclusion criteria, administered at least one dose of assigned product with at least completed one visit will be included in the mITT population.

Safety analysis subset

The safety population will consist of all subjects enrolled in the study, who have received at least one dose of study products i.e. mITT population.

Methods of Analysis

Primary Efficacy and secondary endpoints will be analyzed using the PP & mITT population. And Safety variables as per mITT only.

4 Data Handling

Data entry into CRF must be performed as per general CRF data entry guidelines, summarized at the time of data entry feasibility training. Data entry will be made as per source document without interpretation or modification to maintain consistency and accuracy of the data. Study specific

Confidential & Proprietary

Any unauthorized use, disclosure, distribution or copying of these information is strictly prohibited

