5.1 Descriptive methods

Participant Disposition

Demographic and Baseline Information

Continuous variables that are Age, weight, BMI, and other demographical characteristics will be summarized by overall using summary statistics i.e. the number of observations, mean and standard deviation with 95% CI (among normal distribution) or median with range (if non-normal distribution). Categorical values like gender and clinical Examination will also be summarized using frequencies and percentages.

Confidential & Proprietary

Any unauthorized use, disclosure, distribution or copying of these information is strictly prohibited

The medical history and Physical examination will be presented using frequencies and percentages of subjects for the Safety population. For continuous data student analysis of variance test and for categorical data Chi square test will be estimated to compare the baseline demographical data between groups and changes during the follow up.

5.2 Efficacy Parameters:

Summary of efficacy parameters – the number of observations, mean and standard deviation with 95% CI (among normal distribution) or median with range (if non-normal distribution)

Analysis of Primary Efficacy Parameters

In this study median Time to Clinical Improvement (TTCI) using NEWS Score [Time Frame: First treatment date up to when PCR is negative] TTIC using 7-point ordinal scale [Time Frame: First treatment date up to when PCR is negative] will be assessed for both Test and Placebo group and compare the mean time between two arms by using Mann Whitney U test.

Other variables that are Rate of progression to severe/critical COVID-19 disease based on NEWS score and 7 point ordinal scale [Time frame: First treatment date up to 28 days] will be compared by using Chi Square test.

Other parameter like Time to COVID-19 nucleic acid testing negativity in oropharyngeal/nasal swab) [Time Frame: First treatment date up to 28 days] will be estimated by Student t test or one way analysis of variance. If data is

Confidential & Proprietary

Any unauthorized use, disclosure, distribution or copying of these information is strictly prohibited

not passing normality for continuous variable Mann Whitney test will be assessed instead of student t test.

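### The unadjusted Mann-Whitney test of TTCI (NEWS) ignores whether subjects already meet all six criteria at Day 1, and so loses power

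*Protocol*

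**What the plan says.** **Endpoint.** Protocol synopsis, Primary Endpoints, item 1 (repeated in SAP 2) measures time "from the start of treatment with the study drug / placebo to the persistent achievement of all of the following criteria". The six criteria are temperature below 37 °C without antipyretics, respiratory rate below 22/min, SpO2 above 95% on room air, systolic pressure at most 200 mmHg, pulse 51-90, and being conscious and alert. The note adds: "Persistent achievement means the preservation of each of the criteria for at least 7days". The temperature item is worded "Stopping a fever (which is defined as a decrease in axillary temperature below 37" °C.

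**Entry.** Inclusion criterion 4 reads "Either asymptomatic or have mild symptoms", then "If symptomatic, symptoms are mild (cough, weakness, sore throat" and so on. For symptomatic subjects it already asks for SpO2 above 95%, which is the endpoint's own threshold, and a respiratory rate of not more than 22/min. Nothing requires a criterion to be unmet at Day 1.

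**Analysis.** SAP 3: "Primary Efficacy and secondary endpoints will be analyzed using the PP & mITT population". Neither set separates subjects by Day 1 status. For both TTCI endpoints SAP 5.2 says to "compare the mean time between two arms by using Mann Whitney U test"; it names no stratification or covariate.

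**Schedule.** Vital signs, oximetry, NEWS and concomitant medication are recorded on Day 1. After that, vital signs, oximetry and NEWS are scheduled only on Days 7 and 15, or on the discharge day if earlier.

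**The concern.** Cough, weakness and sore throat are not TTCI criteria. An asymptomatic subject, or one with only those symptoms, can therefore meet all six before the first dose. Others will not, for example with a pulse above 90, a respiratory rate of exactly 22, or a temperature of 37 °C or more.

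A subject who meets and holds all six from the start cannot improve on TTCI and takes the lowest time in either arm. Such ties carry no information on treatment. Chance differences between the arms in their number add noise to the rank comparison. Day 1 status is thus strongly prognostic for TTCI, is fixed before treatment and is already collected, yet the planned test ignores it.

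At stake is a missed effect among subjects who had something to improve, on one of five primary endpoints. If at least half of each arm sits at the lowest value, the median TTCI is that value in both arms and describes nothing.

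**Working it through.** **The plan's own figure.** The protocol's Statistical Analysis row gives 112 (56 per arm) "completed cases needed to assess the study objective at 80% power and 5% level of significance". Adding 10% gives 112 × 1.1 = 123.2, so 124, as printed. The 112 itself cannot be reproduced, because no endpoint or effect is named. Back-solved for two means at two-sided 5% (sidedness is not stated), it corresponds to (1.96 + 0.84) × √(2/56) = 0.53 SD. The runs below use a 0.55 SD shift on log time, which gives the Mann-Whitney test 80.4% power when nobody meets all six at Day 1. Setting TTCI at 80% is an assumption.

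**No loss of a criterion, closed form.** Let p be the share tied at the lowest value in each arm.

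- Unadjusted test: λ = 2.80 × (1−p)² / √(1−p³). Only pairs with both subjects off the floor, a share (1−p)², carry information; 1−p³ is the tie correction.
- Test stratified by Day 1 status: λ = 2.80 × √(1−p). The all-tied stratum adds nothing.
- Power = Φ(λ − 1.96) + Φ(−λ − 1.96).

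Example, p = 0.3: unadjusted λ = 2.80 × 0.49/√0.973 = 1.39, power 28%; stratified λ = 2.80 × 0.837 = 2.34, power 65%.

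| Met and held | Closed form: unadjusted / stratified | Simulated: unadjusted / stratified |
|---|---|---|
| 5% | 71 / 78% | 72 / 79% |
| 10% | 62 / 76% | 64 / 78% |
| 20% | 44 / 71% | 43 / 71% |
| 30% | 28 / 65% | 28 / 66% |
| 50% | 12 / 51% | 11 / 50% |

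The simulations used 56 per arm and 4,000 trials per row (10,000 for 20% and 50%). With no loss, the rank test adjusted for Day 1 status has practically the same power as the stratified test.

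**Type I error.** Null runs with 10, 30 or 50% met, and 0 or 30% loss in both arms, rejected in 4.6-5.1% of trials for the unadjusted, stratified and restricted tests. (Restricted means only subjects failing at least one criterion at Day 1.)

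**Some Day-1-met subjects lose a criterion within 7 days.** 30% met, 0.55 SD shift, and those who lose a criterion take times like the other subjects:

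| Loss, control / active | Unadjusted | Stratified | Restricted |
|---|---|---|---|
| 30 / 30% | 41% | 57% | 65% |
| 30 / 15% | 54% | 74% | 65% |
| 40 / 20% | 63% | 78% | 65% |
| 40 / 10% | 71% | 85% | 64% |

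**Drug acting mainly by preventing loss.** 30% met, 40 / 10% loss, and those who lose a criterion placed 1.5 SD later:

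| Shift | Unadjusted | Van Elteren | Rank test adjusted for Day 1 status |
|---|---|---|---|
| 0.2 SD | 43% | 37% | 52% |
| 0 | 24% | 13% | 27% |

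Here the van Elteren test falls below the planned test. The adjusted rank test was not below the planned test in any scenario with an effect that was run.

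**The case against.** **The scoring is largely settled.** The clock starts at treatment and stops at persistent achievement, so a subject who meets and holds all six gets the lowest time, and the 7-day note already makes an early loss not persistent. This stands. A reader might infer from the word decrease in the temperature item that TTCI is undefined for anyone afebrile at Day 1 and that such subjects drop out of the analysis. The item is a threshold at 37 °C, and neither document says that anyone is dropped. One clarifying sentence is enough.

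**The harm is assumed.** This also stands as to size. The documents give no share met, loss rate or TTCI effect, and the 80% is not tied to TTCI. The share at the floor is of those who meet and hold, which is smaller than the share who meet on Day 1. At 5% met the gap is about 7 points. But asymptomatic subjects belong to the stated study population, so a zero share cannot be presumed.

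**Stratifying is not always better.** Correct for van Elteren, as the last table shows. Prevention of loss is a plausible mechanism in a trial that enrols asymptomatic subjects and lists progression among its primary endpoints. This argues for choosing the method with care; it does not argue for ignoring Day 1 status.

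**The data are sparse.** Holding for 7 days can be judged only at Day 7 and Day 15. The protocol's time frame for this endpoint ends at discharge, which may come before Day 15. That limits any analysis of this endpoint, including the planned one, and leaves one scoring case open (see the fix).

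**Conclusion.** The point holds as one of efficiency and interpretation. Subjects who can already meet every criterion at Day 1 are pooled with those who can improve, in a test that ignores a known and strongly prognostic pre-treatment value. In the illustration the cost is about 7 points of power at 5% met, 14 at 10% and 38 at 30%. This assumes 56 per arm, a 0.55 SD shift acting only on subjects who can improve, and no later loss of a criterion. With loss of criteria the gap is smaller and depends on how the drug works.

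Two stronger conclusions should not be drawn. The planned test does not give false positives: its type I error stays near 5%. Nor do the documents show that the trial is underpowered by any particular amount, since none of the driving quantities is given. Part of the loss (80% down to 66% at 30% met) comes from enrolling subjects who cannot improve on this endpoint, and adjustment does not recover it. This should be fixed before unblinding; it does not threaten validity.

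**What to change.** **In SAP 5.2:**

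1. Classify each subject by whether all six criteria are met at the Day 1 assessment, and state that this assessment precedes the first dose.
2. Replace the unadjusted Mann-Whitney test of TTCI (NEWS) with one prespecified test on all subjects: either rank the whole sample and adjust the arm comparison for Day 1 status, or use a van Elteren test stratified by that status. The first is the safer choice on the runs above.
3. Report by arm how many met all six at Day 1 and how many of those later lost one. Give the comparison restricted to subjects failing at least one criterion as supportive only, because the stated purpose also covers asymptomatic subjects.
4. State that the 7-day hold is judged at the scheduled visits, and how a subject who met all six at Day 1 but is discharged before 7 days is scored.

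**In endpoint 1 (protocol and SAP 2):** say that the temperature item means a reading below 37 °C without antipyretics, whether or not fever was present at Day 1.

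**Cost.** Text changes and a little programming. The Day 1 data are already scheduled; only their pre-dose timing must be stated. SAP 8 names SPSS Version 10.0, so confirm that it can run the chosen test; van Elteren can also be computed from the rank sums within each stratum.

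**Downsides to state.** Neither method restores 80% power. With no loss of a criterion, that would take 56/(1−p) completers per arm: 63, 70, 80 or 112 at 10, 20, 30 or 50% met. Van Elteren can also fall below the planned test if the drug acts mainly by preventing loss of criteria.

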Visits of Assessment	
Screening and 3 visits and one telephonic follow-up
 
Screening Inclusion/Exclusion Criteria, Subject Inform Consent, Demography, Medical History, Physical Examination, Vital Signs, HIV; HBsAg; HCV; Hs-CRP; Pulse oximetry; NEWS scoring; 7- point ordinal scoring; Medication list review (medications being taken for comorbid conditions), Lab assessment; Urine analysis Note: Patients who do not meet the study inclusion exclusion criteria during screening should not be randomized into the study.
 
Day 1 Randomization, Vital Signs, Pulse oximetry, AE/SAE, Concomitant Medication, ViraCide/ Placebo treatment start, NEWS scoring; 7-point ordinal scoring
 
Day 7 Physical Examination, Vital Signs, AE/SAE, Concomitant Medication, ViraCide/ Placebo Compliance check, Pulse oximetry; NEWS scoring; 7-point ordinal scoring. (Note: If the subject is discharged on this day as per PI's discretion and patient's health condition then assessment scheduled for day 15 will be carried out on discharge day).
 
Day 15 Physical Examination, Vital Signs, AE/SAE, Concomitant Medication, ViraCide/ Placebo treatment end, RT-PCR for

	
Sars- Co-V2, Hs-CRP, Safety Lab Tests, Pulse oximetry; NEWS scoring; 7-point ordinal scoring, ViraCide/ Placebo Compliance check, Lab assessment including urine analysis
 
Day 28 Phone call follow up for time :
 
 • until negative RT-PCR for Sars-Co- V2, COVID-19 related mortality, • development of any COVID-19 symptom, • development of any worsening of comorbid condition; • Development of new AE/SAE; Resolution status of previous AE/SAEs 
Note: If subject is discharged before Day 15 on PI's discretion as per patients health condition, then assessments scheduled for Day 15 will be carried out on the discharge day (as far as possible and those not performed will be noted on appropriate CRF page) and Day 15 visit will be done telephonically.

Laboratory Investigations	
Screening: Recording RT-PCR- Sars-Co-V2 result; Urine pregnancy test; HIV; HBsAg; HCV; Hs-CRP; Hematology* + Biochemistry + Urine analysis*; ECG
 
Day 1: No labs
 
Day 7: No labs
 
Day 15: Oropharyngeal/nasal swab for PCR- Sars-Co-V2; Hematology* + Biochemistry + Urine analysis*; ECG; Serological biomarker: Hs-CRP

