STATISTICAL ANALYSIS PLAN

STUDY TITLE:

A DOUBLE BLIND, RANDOMIZED, PLACEBO CONTROLLED

STUDY TO EVALUATE EFFICACY AND SAFETY OF

“VIRACIDE”

IN THE MANAGEMENT OF

CORONA VIRUS DISEASE 2019 (COVID-19)

Version No. – 01

Dated: 04th June 2020

Protocol ID – NS-VC-CT01-20

Clinicaltrial.gov ID: NCT04596085

Confidential & Proprietary

the unauthorized use, disclosure, distribution or copying of these information is strictly prohibited

Confidential

Page

1 of 11

Table of Contents

[1 Definitions](#)

[2 Objectives](#)

[3 Analysis Sets](#)

[4 Data handling](#)

[5 Statistical methods](#)

[5.1 Descriptive methods](#)

[5.2 Primary analysis](#)

[5.3 Analysis of the secondary endpoints](#)

[5.4 Safety and/or further analyses](#)

[6 Listings, tables, figures](#)

[7 Graphs](#)

[8 Software](#)

Confidential & Proprietary

the unauthorized use, disclosure, distribution or copying of these information is strictly prohibited

Confidential

Page

2 of 11

1 Definitions

The following abbreviations will be used in this statistical analysis plan.

ITT	Intention-to-treat
PP	Per protocol
IP	Investigational product
AE	Adverse Event
SAE	Serious adverse event
TTCI	Time to clinical Improvement
SPO2	Oxygen saturation
ICU	Incentive Care Unit

Confidential & Proprietary

the unauthorized use, disclosure, distribution or copying of these information is strictly prohibitea

2 Objectives

Primary Efficacy Endpoint:

1. TICI using NEWS Score [Time Frame: First treatment date up to when PCR is negative]

The median time in days from the start of treatment with the study drug / placebo to the persistent achievement of all of the following criteria:

- Stopping a fever (which is defined as a decrease in axillary temperature below 37 ° C without the use of antipyretic drugs);
- Respiratory rate <22 / min;
- Oxygen saturation (SPO2) > 95% when breathing in atmospheric air. Measured using pulse oximetry
- Systolic blood pressure ≤200 mmHg
- Pulse rate 51-90 beats/minute
- Is conscious and alert

[Note: Persistent achievement means the preservation of each of the criteria for at least 7 days.]

2. TTIC using 7-point ordinal scale
3. Rate of progression to severe/critical COVID-19 disease based on NEWS score [Time frame: First treatment date up to 28 days]
4. Rate of progression to severe/critical COVID-19 disease based on 7-point ordinal scale [Time frame: First treatment date up to 28 days]

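### The 7-point-scale progression endpoint runs to Day 28, but scoring is scheduled only to Day 15 or earlier discharge, and no rule derives later status

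*Protocol*

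**What the plan says.** The Protocol synopsis, Primary Endpoints item 4, reads "Rate of progression to severe/critical COVID-19 disease based on 7-point ordinal scale [Time frame: First treatment date up to 28days". SAP section 2, primary endpoint 4, reads "Rate of progression to severe/critical COVID-19 disease based on 7-point ordinal scale [Time frame: First treatment date up to 28 days". SAP section 5.2 and the table list in section 6 keep the 28-day window, and section 5.2 assigns a chi-square test to the comparison.

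Under Visits of Assessment, the Protocol lists the scoring occasions one by one:

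- Screening: "NEWS scoring; 7- point ordinal scoring; Medication list review"
- Day 1: "treatment start, NEWS scoring; 7-point ordinal scoring"
- Day 7: "Compliance check, Pulse oximetry; NEWS scoring; 7-point ordinal scoring"
- Day 15: "NEWS scoring; 7-point ordinal scoring, ViraCide/ Placebo Compliance check, Lab assessment including urine analysis"

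Day 28 is introduced as "Phone call follow up for time". Its items are time to a negative RT-PCR, COVID-19 related mortality, any COVID-19 symptom, worsening of a comorbid condition, and adverse events. No ordinal or NEWS score is among them. The Study Description calls Day 28 a follow-up visit but gives it no assessments.

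For a subject discharged before Day 15, the Day 15 assessments move to the discharge day as far as possible, and "Day 15 visit will be done telephonically". No content is listed for that call.

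**The concern.** An endpoint defined on a scale needs the scale to be scored, or derived by a stated rule, across its whole window. Here the scheduled scores stop well before the window closes. They stop earlier still for subjects discharged early, so the length of scored follow-up depends on the discharge date.

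Two things are at stake. The first is the label: a primary result reported as a 28-day progression rate could in fact describe the period to Day 15 or discharge. The second is discretion: with no derivation rule, the analyst must decide how to treat the unscored period after the data exist. Late status could be set to not progressed, treated as missing, or inferred from ICU, ventilation, death or adverse event records. These choices can give different rates for a primary endpoint.

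**Working it through.** **1. Window against schedule.**

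| Contact | 7-point score listed? |
|---|---|
| Screening | Yes |
| Day 1 | Yes |
| Day 7 | Yes |
| Day 15 (or discharge day, if earlier) | Yes |
| Day 15 call after early discharge | No content listed |
| Day 28 call | No |

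Unscored part of the window = (28 − day of last score) / 28.

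- Last score on Day 15: (28 − 15)/28 = 13/28 = 46%.
- Discharge on Day 7, which the Day 7 entry expressly allows for: (28 − 7)/28 = 21/28 = 75%.

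These are shares of calendar days, not of events.

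**2. Is there another route to a later score?** ICU admission, survival and mechanical ventilation are secondary endpoints to Day 28, and the Day 28 call asks about COVID-19 mortality and adverse events. Neither document defines the seven levels or the severe/critical threshold, and neither maps those events to the scale. SAP section 5.2 gives the test and nothing on the unscored period.

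**3. The same check on NEWS.** The Protocol gives the NEWS progression endpoint a window of 15 days, which ends at the last scheduled score. SAP sections 2, 5.2 and 6 give it 28 days. NEWS follows the same visit schedule, so the SAP's version has the same gap and also disagrees with the Protocol.

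**4. The plan's own figures.** The Protocol's Statistical Analysis entry needs 56 completers per arm and enrols 62 per arm for 10% dropout: 56 × 1.10 = 61.6, rounded up to 62, so 124 in total. This reproduces. (Dividing by 0.90 gives 62.2, or 63 per arm, a trivial difference.) The 80% power cannot be reproduced, because no event rate or effect size is given.

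**5. Illustration of lost events.** Inputs: 56 per arm from the Protocol; 5% significance from the Protocol, taken as two-sided because sidedness is not stated; 28-day progression rates of 30% v 10%, assumed; a fraction f of events after the last score, assumed equal in both arms and captured by no route. Observed rates are 0.30 × (1 − f) and 0.10 × (1 − f). Power is the summed binomial probability of all outcome pairs with a Pearson chi-square of at least 3.84.

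| f | Observed rates | Power |
|---|---|---|
| 0 | 30.0% v 10.0% | 78.1% |
| 5% | 28.5% v 9.5% | 75.4% |
| 10% | 27.0% v 9.0% | 72.4% |
| 20% | 24.0% v 8.0% | 65.8% |

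**The case against.** The strongest reply is that the endpoint concerns severe or critical disease, and the gravest late events would be known. ICU admission, ventilation and survival are followed to Day 28, the call asks about mortality and adverse events, and the Protocol's entry on stopping study drug itself associates severe COVID-19 with ICU admission and ventilation. Worsening below the severe/critical threshold would not be an event in any case.

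Much of this stands. A reader might infer that the endpoint cannot be measured after Day 15, but the documents do not support that. What they show is that no score is scheduled and no derivation is given. The reply does not close the gap, however. The events are separate endpoints with no stated link to the scale, ICU admission and ventilation are not listed items of the call, and the undefined threshold leaves open whether some severe categories fall short of them.

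A reader might also infer that anyone who worsens late will be counted as not progressed. Neither document says so; the handling is unspecified.

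Finally, the power figures might be read as an expected loss. They are not. The rates and late fractions are assumptions, the subjects enter asymptomatic or mild, and the calculation supposes that no late event is picked up by any route. At a 5% late fraction the loss is under 3 points.

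**Conclusion.** The mismatch is real and rests only on the visit list and the endpoint wording. Both documents set a 28-day window, scoring stops at Day 15 or discharge, and no rule supplies later status. Scored from the planned assessments, the result would leave 13 of 28 days uncovered, or 21 of 28 for a Day 7 discharge.

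The number of events this would lose cannot be determined from the documents. The fall in power from 78% to between 75% and 66% is an illustration under the stated assumptions; the mislabelled window does not depend on it. The point affects one of five primary endpoints, plus NEWS progression as the SAP words it. It should be corrected, and the correction is cheap.

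**What to change.** 1. At the Day 28 call, and at the Day 15 call for subjects discharged early, record the worst 7-point category since the last score. Status on the day of the call is not enough, because it would miss a subject who worsened and recovered in between.
2. State in the SAP how death, ICU admission and mechanical ventilation up to Day 28 map to the scale and count toward the endpoint. This requires the levels and the severe/critical threshold to be written down.
3. If the scale cannot be scored by phone, restate the window in both documents as up to Day 15 or discharge, whichever is earlier, and report events after Day 15 only through the existing 28-day secondary endpoints. A window of Day 15 alone would not cover early discharges, whose last score is on the discharge day.
4. Reconcile the NEWS progression window, which is 15 days in the Protocol and 28 days in the SAP.

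The cost is one added item on calls already planned and a short SAP rule, or a wording change. The small downside is that worst status reported by phone is coarser than an in-person score.
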